Screening for child mental health conditions. The Strengths and Difficulties Questionnaire¹³¹ is a 25-item scale widely used as a screening tool for mental health in numerous LMIC settings¹³², including SSA¹³³. The SDQ will be used beginning at age 3. The SDQ includes 4 difficulty scales (emotional symptoms, conduct problems, hyperactivity/inattention, and peer relationship problems) and a scale for prosocial behavior. The Strengths and Difficulties Questionnaire¹³¹ is a 25-item scale widely used as a screening tool for mental health in numerous LMIC settings¹³², including SSA¹³³. The SDQ will be used beginning at age 3. The SDQ includes 4 difficulty scales (emotional symptoms, conduct problems, hyperactivity/inattention, and peer relationship problems) and a scale for prosocial behavior. SDQ scales had good internal consistency in African studies¹³⁵⁻¹³⁹, although the hyperactivity/inattention scale has performed less well¹³⁸. Poor SDQ scores correlated with expected demographic characteristics in South Africa and Uganda¹³⁷. A z-score corresponding to the 80th-90th and >90th percentiles have been considered borderline and indicative of 'caseness'¹³⁶, and will prompt further screening.

Hearing: We will use combined otoacoustic emission (OAE) and auditory brainstem response (ABR) screening tests to assess hearing. Infants will be screened at 6 weeks using OAE and referred for ABR if they screen positive. At age 3 and 4 years, we will use a smart phone based hearing screen (Hearscreen TM) to assess hearing. These tests are non-invasive and does not involve input of energy into the body.

Summary table for aim 1 data collection

	Enrollment	Month 6	Month 12	Month 18	Month 24	Month 30	Month 36	Month 42	Month 48
Consent	X								
Locator data	X	X	X	X	X	X	X	X	X
Medical history	X	X	X	X	X	X	X	X	X
Anthropometry	X	X	X	X	X	X	X	X	X
MDAT	X	X	X	X	X	X	X	X	X
SDQ							X	X	X
ASD screen				X	X				X
Hearing screen	X						X		X
DBS	X		X		X		X		X

vii. Sample size determination & data analysis

For **all analyses**, *a priori* cofactors of interest in the multivariate analysis include household sociodemographic factors, birthweight, preterm birth, maternal depression, infant sex, maternal education, and infant/child LAZ. Collinearity will be examined using standard error assessments and multivariate models will include non-collinear variables associated with growth in univariate model ($p < 0.05$).

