Mortality, infectious morbidity, and hospitalizations: Cox regression will be used to compare survival of the HEU and HUU cohorts and to determine predictive factors for mortality overall and stratified by HEU/HUU. During the 4-year follow-up period for the aim 1 cohort, incidence of hospitalization, severe pneumonia, and diarrhea will be calculated and compared between HEU and HUU cohorts as number of events over person-time of follow-up with censoring for mortality and loss to follow-up. Predictors of first morbidity (separate analyses for pneumonia, severe diarrhea, and hospitalizations) will be identified using Cox proportional hazards regression with censoring for mortality and loss to follow-up.

Analysis: We will compare MDAT social, motor and language scores and prevalence of ASD between HEU and HUU and among HEU by maternal VL detection in pregnancy, maternal pre-conception ART, and by ART regimen. The percentage of normal, borderline and high scores on the SDQ will be calculated for the domains: emotional problems, conduct problems, hyperactivity, peer problems, and prosocial behavior and for total difficulty. Univariate and multivariate logistic regression will be used to determine whether HEU vs. HUU is associated with higher likelihood of high scores on SDQ domains overall. Among HEU, we will assess influence of maternal VL, ART, and regimen. Multivariate analyses will be adjusted for maternal sociodemographic factors and depression and infant birthweight and growth.

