R33 Aim 2				
Difference in BENC1 scores	0.29	1000 HEU: 100 HUU age stratum (7-11yo)		SD=1.0
Difference in ADHD prev.	7.7%	1000 HEU: 100 HUU		2.7% in HUU ¹⁷⁵
Difference in depression prev	10.1%	1000 HEU: 100 HUU per age stratum		HUU 10%

Analyses: For binary outcomes such as ADHD and depression, multivariate generalized linear models (GLM) with log link and binomial family for relative risk estimation clustered by site will be used. For continuous variables such as NIH-Toolkit, we will use multivariate GLM with Gaussian family and identity link. As previously noted in Aim 1, we will include *a priori* potential confounders - maternal depression, preterm birth, and infant birthweight - in multivariate analysis, after assessment of collinearity.

MDAT (social, fine motor, gross motor, language)	GLM
Hearing	GLM
BENCI (processing speed, visual-motor coordination, attention, language, memory, executive function)	GLM
SDQ total domain score	GLM
ADHD screen (analyze positive SNAP-IV and subset validated on MINI-Kid)	GLM
PHQ-9 (prevalence of moderate-severe symptoms)	GLM
Neuropsychiatric diagnoses	GLM

Training procedures for aim 1 and 2

The study team will develop protocols and training materials for clinic staff. A 5-day training workshop will be designed. The package will include the basics of early childhood development, pediatric mental health, screening and use of the study screening and diagnostic tools. The training will cover neurodevelopmental assessments, psychometric testing, and administration, scoring and interpretation of the MDAT and NIH Toolbox. The 5-day nurse training workshop will cover general sensitization to the testing situation, including ensuring that the child follows the instructions, methods of cross-checking to determine whether a child understood instructions, learning when to give breaks, how to re-engage the child and how to react to distress. The training will cover how to recognize need for referrals and provide motivational interviewing and culturally sensitive assessment skills. To ensure quality control, the study coordinator will conduct refresher training for staff to ensure operating procedures are followed consistently. We will also develop checklists for tests requiring multiple tests as well as the use of tablet based tests to ensure quality assessments.

e. Aim 3

i. **Study design**

This Aim of the study involves 2 cross-sectional components:

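### The Aim 1 SDQ outcome counts a high score as adverse on every domain it lists, including prosocial behaviour, where a high score is favourable

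*Protocol*

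**What the plan says.** Protocol section 12.c.vi (Aim 1 data collection instruments, on screening for child mental health conditions) describes the instrument: "The SDQ includes 4 difficulty scales (emotional symptoms, conduct problems, hyperactivity/inattention, and peer relationship problems) and a scale for prosocial behavior". The same paragraph gives one percentile rule, in the upper direction only: "A z-score corresponding to the 80th-90th and >90th percentiles have been considered borderline and indicative of" caseness respectively. It adds that such scores lead to further screening. It makes no exception for the prosocial scale.

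Section 12.c.vii (Aim 1, the paragraph headed Analysis) turns the SDQ into an outcome: "The percentage of normal, borderline and high scores on the SDQ will be calculated for the domains". The list that follows covers emotional and conduct problems and then "hyperactivity, peer problems, and prosocial behavior and for total difficulty". The logistic model is to determine "whether HEU vs. HUU is associated with higher likelihood of high scores on SDQ domains overall". The next sentence adds comparisons within HEU by maternal viral load, ART and regimen.

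The protocol states no reverse scoring, low-tail cut-off or exclusion for the prosocial scale.

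**The concern.** The protocol contrasts scales that measure difficulty with one that measures prosocial behaviour. More of the first is worse; more of the second is better. Yet one outcome category, *high*, and one direction of test, more *high* in HEU, are applied to both kinds of scale.

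The stake is the sign of one domain's result. The study is meant either to detect mental-health harm from fetal HIV and ART exposure or to give credible reassurance. If HEU children were less prosocial, the written outcome would report fewer high scores in HEU, which reads as protection. If the word *overall* in the model sentence means a single outcome of a high score on any domain, four adverse indicators and one favourable indicator would be mixed, and the pooled effect would be distorted. The within-HEU comparisons would inherit the problem if they use the same outcome.

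**Working it through.** **1. The plan's own SDQ figure.** The effect-size table in section 12.d.vii gives a detectable difference in SDQ-positive prevalence of 5.2% at 1000:1000 and 5.9% with 20% attrition, for 20% in HUU, 80% power and alpha 0.05. I take alpha as two-sided, which the protocol does not state. The formula is

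n per group = [1.960·√(2p̄(1−p̄)) + 0.842·√(p₁(1−p₁) + p₂(1−p₂))]² / (p₂−p₁)²

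Solving for p₂ with p₁ = 0.20:

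| n per group | Recomputed | Stated |
|---|---|---|
| 1000 | 5.24% | 5.2% |
| 800 | 5.89% | 5.9% |
| 500 | 7.53% | 7.5% |
| 400 | 8.48% | 8.5% |

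These reproduce. The point concerns direction, not sample size.

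**2. Direction of the prosocial odds ratio.** Assumptions, none of them from the protocol: the prosocial score is normal with SD 1, and HEU are shifted by d towards less prosocial behaviour. The cut c is set so that a fraction p₀ of HUU lies beyond it. I use p₀ = 10% (c = 1.2816), matching the 90th percentile in section 12.c.vi, and p₀ = 20% (c = 0.8416), matching the 80th percentile and the 20% HUU prevalence in the effect-size table.

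- Rule as written: P(high in HEU) = 1 − Φ(c + d)
- Adverse tail: P(low in HEU) = Φ(−c + d)
- OR = [p/(1−p)] / [p₀/(1−p₀)]

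Worked case, d = 0.2 and p₀ = 10%:
- High: 1 − Φ(1.4816) = 0.0692. OR = (0.0692/0.9308)/(0.10/0.90) = 0.67.
- Low: Φ(−1.0816) = 0.1397. OR = (0.1397/0.8603)/(0.10/0.90) = 1.46.

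| d (SD) | p₀ | High in HEU | OR as written | Low in HEU | OR, adverse tail |
|---|---|---|---|---|---|
| 0.1 | 10% | 8.4% | 0.82 | 11.9% | 1.21 |
| 0.2 | 10% | 6.9% | 0.67 | 14.0% | 1.46 |
| 0.3 | 10% | 5.7% | 0.54 | 16.3% | 1.75 |
| 0.1 | 20% | 17.3% | 0.84 | 22.9% | 1.19 |
| 0.2 | 20% | 14.9% | 0.70 | 26.1% | 1.41 |
| 0.3 | 20% | 12.7% | 0.58 | 29.4% | 1.67 |

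Under this shift model, any d above zero puts the as-written OR below 1 and the adverse-tail OR above 1. The size depends on d; the reversal does not.

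**3. Chance of a significant result in the wrong direction.** For d = 0.2, the same two-proportion formula gives the power of the as-written comparison:
- 10% cut: about 70% at 1000:1000 and 60% at 800:800.
- 20% cut: about 86% at 1000:1000 and 77% at 800:800.

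These ignore clustering by site and covariate adjustment.

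**The case against.** The strongest reply is that *high* is loose wording for *abnormal*. The SDQ is a standard instrument, section 12.c.vi itself speaks of poor scores, and a scoring manual or an analysis plan not shown here may reverse the prosocial scale. That may well be what would happen, and it is why the wrong sign is a consequence of following the text, not a certainty. It does not remove the point. The protocol does not leave direction open: it names the category, lists prosocial behaviour under it, and states which direction is to be tested. An analysis plan that scored the scale properly would depart from that text.

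It can also be said that the percentile rule in section 12.c.vi reports a cited source, and that the text does not say whether it applies to each subscale or only to the total. That stands. Whether highly prosocial children would actually be sent for further screening is therefore inference, and the passage needs reconciling, not correcting.

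The word *overall* may mean only the whole cohort, as against the within-HEU sentence that follows. The pooled-outcome problem is therefore conditional on that reading.

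Two stronger readings are tempting and are not supported:
- A reader might infer that the Aim 2 outcome listed as "SDQ total domain score" sums all five scales. The Aim 2 tool table in section 12.d.vi lists only the four difficulty domains for the SDQ, and the text there names the Total Difficulties Score as the aggregate.
- A reader might infer that children with low prosocial scores could never be picked up for further screening. They can still screen positive on the difficulty scales or the total. At most, a low prosocial score alone would not trigger it.

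Finally, the consequence is limited. The SDQ is not among the outcomes in Table 6, and prosocial behaviour is one of six SDQ summaries.

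**Conclusion.** The point holds for the prosocial domain in the Aim 1 analysis. Followed literally, the stated outcome treats favourable prosocial scores as adverse, and an HEU deficit would appear as protection. For an assumed 0.2 SD deficit the odds ratio is about 0.67 instead of 1.46 with a 10% cut, and about 0.70 instead of 1.41 with a 20% cut. These sizes rest on a normal score, a pure shift in mean and a deficit that the documents do not supply.

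That a high prosocial score is favourable is not stated outright; it follows from the protocol's own contrast between difficulty scales and the prosocial scale. The four difficulty scales, total difficulty, the SDQ detectable differences and the primary MDAT outcome stand as they are. The change should be made, but it does not threaten the study's main conclusion.

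**What to change.** In the Aim 1 Analysis paragraph of section 12.c.vii:
- Replace *high* with *abnormal* in both the descriptive sentence and the model sentence.
- Define the adverse direction per scale: upper tail for the four difficulty scales and total difficulty; lower tail, or reverse-scored, for prosocial behaviour.
- Analyse prosocial behaviour separately from any overall or total-difficulty outcome, and say what *overall* means.

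In section 12.c.vi, reconcile the upper-percentile caseness and further-screening wording with the distinction the same paragraph draws between difficulty scales and the prosocial scale. The choice of screening trigger is the sponsor's.

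The cost is wording in two places and one line of scoring code. No new data are needed and the sample size does not change.

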Cognitive outcomes. Cognitive assessments will be done using NIH Toolbox. The battery will include the tests Dimensional Change Card Sort Test, Flanker Inhibitory Control and Attention Test, List Sorting Working Memory Test, Pattern Comparison Processing Speed Test, and Picture Sequence Memory Test, which evaluate working memory, attention, processing speed, and other aspects of executive functioning. The NIH Toolbox has been validated for US children and was recently adapted through a rigorous process involving translation and backtranslation for Kenya, including translation to Dholuo and Kiswahili.

The table below summarizes the tools, age-group they are used in, screening time and domains or disorders they test.

Tool	Age-group	Time (minutes)	Types	Domains/Disorder
MDAT	0.6-5	30	Screening	Gross motor, fine motor, language, social
HearScreen TM	3+	5	Screening	Hearing
NIH Toolbox	6-17	25-30	Screening	working memory, attention, processing speed, executive functioning
Strengths and difficulties questionnaire (SDQ)	3-16 & caregivers	10	Screening	Emotional symptoms, conduct problems, hyperactivity/inattention, peer relationship problems
SNAP-IV	6-12	5-10	Screening	ADHD
PHQ-9	>16 & caregivers	3	Screening	Depression
MINI-KID	6-17	10	Diagnostic	Common psychiatric conditions
MINI	18	10	Diagnostic	Common psychiatric conditions
School performance	>10	1	NA	National exam results Parental report

vii. Sample size determination & data analysis

Effect size calculations: For comparisons of z-scores in MDAT or NIH-toolkit scores, we will be able to detect differences of 0.13-0.18 assuming a standard deviation of 1.0 or 1.4, 80% power and alpha of 0.05 in Aim 1 cohort (Table 10). In the cross-sectional cohort, 2- to 3-fold differences will be detectable, in diagnoses such as depression and ADHD. To detect smaller differences, more HUU could be enrolled in some age-strata based on pilot feasibility.

R61/R33 Aim 1 cohort	Effect detectable (no attrition)		Effect detectable (20% attrition)	Assumptions
Difference in z-score for MDAT	0.13 (SD=1.0)	1000 HEU:1000 HUU	0.14 (SD=1.0)	Standard deviation = 1.0-1.4 ¹⁰⁵
	0.18 (SD=1.4)		0.20 (SD=1.4)	
Difference in ASD prevalence	2.2%	1000 HEU:1000 HUU	2.5%	HUU ASD 2%
	3.3%	500 DTG: 500 EFZ	3.8%	
Difference in SDQ+ prev.	5.2%	1000 HEU:1000 HUU	5.9%	HUU SDQ+ 20%
	7.5%	500 DTG: 500 EFZ	8.5%	
Difference in hearing loss	1.7%	1000 HEU:1000 HUU	2.0%	HUU 1%
	2.7%	500 DTG: 500 EFZ	3.1%	
Difference in TL	0.18	500 HEU: 500 HUU		SD=1.0

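### Aim 1 names only a high-versus-not logistic model for the SDQ, which discards information in the score, and the SDQ effect-size row appears to refer to a different cut from the one modelled

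*Protocol*

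**What the plan says.** All places are in the Protocol.

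- **Section 12.c.vii (Aim 1), Analysis paragraph.** SDQ results are summarised as percentages normal, borderline and high, for five domains and for total difficulty. Univariate and multivariate logistic regression then examines "whether HEU vs. HUU is associated with higher likelihood of high scores on SDQ domains overall". For maternal VL, ART and regimen among HEU, the paragraph says that their influence will be assessed and names no model.
- **Section 12.c.vi (Aim 1), child mental health screening.** The SDQ has 25 items. On the bands: "A z-score corresponding to the 80th-90th and >90th percentiles have been considered borderline and indicative of 'caseness". Scores in these bands lead to further screening.
- **Section 12.d.vii, effect-size table.** The row "Difference in SDQ+ prev" assumes 20% SDQ+ in HUU. For "1000 HEU:1000 HUU" it gives 5.2 points, or 5.9 with 20% attrition. For 500 DTG v 500 EFZ it gives 7.5 and 8.5. The accompanying text specifies "80% power and alpha of 0.05 in Aim 1 cohort".
- **Section 12.d.vii (Aim 2), Analyses table.** The SDQ entry is "SDQ total domain score", analysed by GLM with no family stated in that row.
- **Table 6 (Aim 1).** MDAT is analysed by linear regression of z-scores. The SDQ is not listed as a primary or secondary outcome.

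**The concern.** There are two separate matters.

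**Loss of information.** Reducing a 25-item score to high or not high ignores all variation within each side of the cut. The stated use of the bands is to trigger further screening, which is a reason to classify children for referral but not a reason to compare groups only on the classification. The protocol keeps MDAT continuous and appears to keep the SDQ as a score in Aim 2. Apart from the ASD screen, the SDQ is the only child mental-health measure in the Aim 1 cohort. If exposure produces a general shift in symptoms, the planned model is less likely to detect it, and a null result could be taken as reassurance. The Aim 1 and Aim 2 SDQ results would also be on different scales, although the Literature review section wants consistency between the cohorts to support causal inference.

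**Mismatch of cut.** The detectable difference is worked out at a 20% rate. The regression is for high scores, which the summary categories separate from borderline. On the protocol's percentiles these are different cuts, so the effect-size row may not describe the analysis it is meant to support.

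**Working it through.** **Inputs from the Protocol:** alpha 0.05 (taken as two-sided, which reproduces the table); power 80%; HUU SDQ+ 20%; 1000 per group, or 800 after 20% attrition; 500 and 400 per group for DTG v EFZ; borderline at the 80th to 90th percentile and caseness above the 90th.

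**Assumption not in the Protocol:** the SDQ total score is normal with SD 1, and HEU differ from HUU by a constant shift.

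**1. The plan's own figure.** For two proportions, with p̄ the mean of p1 and p2:

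power = Φ{[(p2 − p1) − 1.96·√(2p̄(1−p̄)/n)] / √([p1(1−p1) + p2(1−p2)]/n)}

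With p1 = 0.200, p2 = 0.252, n = 1000 and p̄ = 0.226: (0.052 − 1.96 × 0.01870)/0.01867 = 0.82, and Φ(0.82) = 79.4%. The exact 80% difference is 5.24 points, which rounds to the stated 5.2. The other three entries also reproduce: 5.89 (n = 800), 7.53 (n = 500) and 8.48 (n = 400). The table is correct for a 20% rate.

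**2. The same effect as a shift in the score.** d = Φ⁻¹(0.252) − Φ⁻¹(0.200) = −0.668 + 0.842 = 0.173 SD.

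**3. Power on the total score.** Φ(d/√(2/n) − 1.96) = Φ(0.173/0.0447 − 1.96) = Φ(1.92) = 97.2%. About 523 per group would give 80%, against about 1015 for the comparison at the 20% cut.

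**4. Power at a cut above the 90th percentile.** HUU 10.0%; HEU Φ(−1.282 + 0.173) = 13.4%. The formula in step 1 gives (0.0339 − 1.96 × 0.01437)/0.01435 = 0.40, and Φ(0.40) = 65.5%.

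**5. Other group sizes, at the plan's own differences**

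| n per group | HUU v HEU (or regimens), 20% cut | Power, 20% cut | Power, 10% cut | Power, score |
|---|---|---|---|---|
| 1000 | 20% v 25.2% | 79.4% | 65.5% | 97.2% |
| 800 | 20% v 25.9% | 80.2% | 66.5% | 97.4% |
| 500 | 20% v 27.5% | 79.7% | 66.2% | 97.1% |
| 400 | 20% v 28.5% | 80.2% | 67.0% | 97.2% |

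**6. Sensitivity to the assumed distribution** (simulated, 1000 per group, power at the 20% cut about 79% throughout):

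| Pattern of effect | Power on the score |
|---|---|
| Skewed (gamma) score, scale effect | 94% (t-test), 90% (rank test) |
| Skewed (negative binomial) score | 94–96% (mean comparison), 89–95% (rank test) |
| Skewed (gamma) score, constant shift | above 99% |
| Only a subset moved from below the cut into the top fifth | about 51% (t-test) |

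**7. Detectable difference if the modelled rate is 10%.** Solving step 1 for 80% power with p1 = 0.10 gives 4.1 points (n = 1000), 4.6 (n = 800), 5.9 (n = 500) and 6.7 (n = 400).

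Clustering by site, covariate adjustment and the three SDQ visits (Months 36, 42 and 48) are left out of these calculations.

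**The case against.** **The 79% is not a shortfall.** A reader might infer that the plan promised more power than it has. It did not: power at a difference chosen to give 80% is 80% by construction, and 79.4% is only the rounding of 5.24 to 5.2. This objection stands in full.

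**The 97% and 66% are not properties of the plan.** They need a normal score and a uniform shift, and the protocol gives no SDQ mean, SD or distribution. The background is concerned with disorders, for which an effect in a vulnerable subset is plausible, and in that case the cut performs better than the mean. This stands, and it is why a score model should join the logistic model and not replace it.

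**Prevalence is a legitimate target.** The bands are referenced and not data-driven, and the likelihood of a high score speaks to the burden and screening questions put to stakeholders. This stands as a reason to keep the logistic model. It does not explain why that model is the only one named.

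**The text can be over-read.** One might infer that the within-HEU comparisons are also tested only by logistic regression, but no model is named for them. One might take Aim 2 as certainly continuous; the entry's wording suggests so, but GLM in that table also covers binary outcomes. Neither stronger reading is supported.

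**The mismatch is inferred.** The Analysis paragraph does not define high, and the table does not define SDQ+ or say that 20% is a percentile cut. It could be an expected prevalence above some fixed threshold, and then the 66% would not apply. The percentile reading is nevertheless the only one for which the protocol supplies figures.

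**Domain scores.** Twenty-five items over five scales average five items each. The power figures above do not carry over to such short scales.

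**Conclusion.** The point holds in a limited form. For HEU v HUU in Aim 1 the protocol names only a logistic model of high SDQ scores, which discards information. Under an assumed normal score with a uniform shift, the plan's own effect of 0.17 SD has about 97% power on the total score, about 79% at the 20% cut and about 66% at a 10% cut. In the skewed cases tested the score retained at least 89%. With an effect confined to the upper tail the advantage reversed, to about 51% on the score.

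Separately, the 20% SDQ+ assumption fits borderline or above, while high fits about 10%, so the stated detectable differences appear to belong to a different cut from the one modelled. That inference rests on the protocol's percentiles and not on an assumed score distribution.

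The effect-size arithmetic itself is correct. Importance is modest: the SDQ is outside Table 6, and the primary MDAT outcome is already analysed on its continuous scale.

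**What to change.** **Section 12.c.vii, Analysis paragraph.** Add a linear model with robust standard errors for the SDQ total difficulties score, for HEU v HUU and for the within-HEU comparisons. Keep the normal, borderline and high percentages and the logistic model alongside it, so that a tail effect is still covered. Treat score models for the individual domains as supportive only.

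**Section 12.d.vii, effect-size table.** Do one of the following:
- state that SDQ+ means borderline or high, and use that cut in the logistic model; or
- restate the row for high scores at an assumed 10% in HUU: about 4.1 points (4.6 with 20% attrition) for HEU v HUU, and about 5.9 (6.7) for DTG v EFZ.

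**Cost.** Wording only, with no new data, visits or participants. The downside is that a mean difference is less directly clinical than a prevalence; retaining the categories meets this.

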For all aims, the study nurse will provide an in-depth explanation of the purpose and procedures of the study, in the language of the woman's choosing, answer any questions the woman may have, and invite the woman to participate in the study. Mothers will be informed that their participation is voluntary and that participation or nonparticipation in the study will in no way alter the nature of health care services that they receive. If interested in participating, the study nurse will screen HEU and HUU mother-infant pairs for eligibility, and, if eligible, woman will provide written consent for enrollment. If the participant is not literate, a witness unrelated to the study will be present and the consent will be read aloud. The participant will provide oral consent with a witnessed thumbprint documented as consent. This system of recruitment has been highly successful in past and ongoing studies conducted by the research team.

HOPE study protocol

Version 1.3

July 21, 2020

Eligibility criteria

Inclusion criteria:

- Infant age 6 weeks (+/- 2 weeks)
- Healthy infant as determined by study nurse
- Mother age ≥ 18
- Planning to remain in study catchment area for 4 years

Exclusion criteria:

- Infant HIV positive
- Mother HIV status unknown (determined using mother-baby maternal and child health booklet)
- Caregiver planning to relocate

iv. Enrollment and study procedures

Data: At enrollment, contact information, maternal sociodemographic characteristics, adverse childhood events (ACEs), depression (maternal PHQ9), obstetric and medical history, and infant birth history and anthropometrics will be assessed. Medical records from MCH/CCC and viral load records will be abstracted from existing data sources. Maternal HIV status will be determined using mother-baby maternal and child health booklet; if the mother has not been tested for HIV, she will be offered HIV testing.

At every visit, study staff will perform anthropometric measurements (height/weight/head circumference, MUAC), neurodevelopmental and mental health assessments, and collect data on past and current child comorbidities and nutrition.

Summary of procedures for recruitment and enrollment

1. MCH nurse reads recruitment script to potential participant
2. MCH nurse refers interested participant
3. MCH nurse documents reason for declining to participate
4. Study nurse assesses eligibility
5. Study nurse gives more information on the study

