Telomere length analyses Telomere length (TL) may reflect prior fetal exposure to inflammation. In one study PHIV had significantly shorter TL than HEU and HUU children; untreated PHIV had shorter TL than those on ART¹⁶⁰. Among HEU infants, TL was significantly shorter among those whose mothers were untreated in pregnancy than those whose mothers received zidovudine monotherapy and maternal viremia was inversely associated with infant TL¹⁶¹. TL was significantly shorter in South African PHIV (ART-treated) and HEU children than in HUU (mean age 6.4 years)¹⁶². However, not all studies have demonstrated associations between HEU and TL. One study found no difference in TL between PHIV, HEU, and HUU children, although TL shortening was associated with viremia in PHIV¹⁶³. Similarly, there were no significant differences in TL between HEU and HUU children in a recent Canadian study¹⁶⁴. There is also evidence that maternal IPV or adverse childhood experiences (ACEs) influence infant TL^{165,166}. This evidence is limited by differences in exposure and outcome measurements¹⁶⁷⁻¹⁶⁹. TL shortening has been associated with emotional processing on fMRI¹⁷⁰ and with ADHD and depression¹⁷¹⁻¹⁷⁴. **A molecular signal such as TL shortening could reflect ‘archived’ history of fetal HIV exposure to further support associations with HEU.** *Telomere length assessment:* DNA will be extracted from DBS in the University of Nairobi Pediatric Research laboratory prior to shipping to the [name] lab for TL assessment; the [name] lab has extensive experience conducting TL assays. Methods for TL assessment using DBS have been recently developed by Rej et al (*in press*) in the UW [name] lab, who has shared these methods with the [name] lab. Analysis: We will compare TL from 500 HEU and 500 HUU in Aim 1 cohort at 6 weeks, 1, and 4 years of age and compare TL between infants with neurodevelopmental compromise (or with ASD) to those without; overall, and stratified by HEU/HUU status. DBS will be collected in cross-sectional survey of older HEU from 20 sites for future studies, conditional on evidence from Aim 1 results. We will use linear regression to compare TL in HEU to HUU and conditional linear regression for comparisons of neurodevelopmental outcomes; with multivariate adjustment for cofactors as previously described.

d. Aim 2

i. Study design

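### The Aim 1b telomere-length model leaves out maternal ACEs, which the protocol records and cites as a possible influence on infant telomere length, and takes its covariates from a list and an entry rule geared to growth

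*Protocol*

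**What the plan says.** Five statements in the Protocol bear on this.

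- Section 12.c.vii, Telomere length analyses, on what affects infant TL: "There is also evidence that maternal IPV or adverse childhood experiences (ACEs) influence infant TL". The next sentence qualifies this: "This evidence is limited by differences in exposure and outcome measurements".
- The same paragraph plans linear regression of TL on HEU status in 500 HEU and 500 HUU children, "with multivariate adjustment for cofactors as previously described". No TL-specific covariate set is given.
- The start of section 12.c.vii gives the a priori cofactors for all analyses: "household sociodemographic factors, birthweight, preterm birth, maternal depression, infant sex, maternal education, and infant/child LAZ". It then states the entry rule: "multivariate models will include non-collinear variables associated with growth in univariate model", at p < 0.05.
- The analysis paragraph just before the TL paragraph gives a shorter set: "Multivariate analyses will be adjusted for maternal sociodemographic factors and depression and infant birthweight and growth".
- Section 12.c.iv lists the enrolment data: "maternal sociodemographic characteristics, adverse childhood events (ACEs), depression (maternal PHQ9), obstetric and medical history". ACEs appear there as their own item, apart from sociodemographic characteristics and depression. With infants aged 6 weeks, the item can only sensibly refer to the mother.

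**The concern.** The TL paragraph names a possible cause of short infant TL other than HIV or ART, the study measures it, and the model then does not use it. Neither covariate set in section 12.c.vii contains ACEs, and no analysis in the protocol uses them. The only data-driven route into a model is association with growth, which is the wrong criterion for a TL outcome.

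This matters because of how the result will be read. The protocol wants TL shortening to serve as a stored molecular record of fetal HIV exposure, supporting the other HEU findings. That reading is weaker if maternal childhood adversity is an open rival explanation. A mother's ACEs precede the pregnancy, so they are a candidate confounder and do not lie on the path from fetal HIV or ART exposure to TL.

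**Working it through.** **1. Does the adjustment set contain ACEs?** The TL paragraph refers back to cofactors already described. The full list covers household sociodemographic factors, birthweight, preterm birth, maternal depression, infant sex, maternal education and LAZ. The shorter set covers sociodemographic factors, depression, birthweight and growth. ACEs are in neither. They cannot be read into sociodemographic factors, because section 12.c.iv lists the two separately. Under the entry rule, ACEs would come in only if they were associated with growth.

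**2. The protocol's own figure.** The effect-size table in section 12.d.vii gives a detectable TL difference of 0.18 for 500 vs 500 and SD 1.0, with 80% power and alpha 0.05 (two-sided assumed).

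- SE = sqrt(2/500) = 0.0632
- Detectable difference = (1.960 + 0.842) × 0.0632 = 0.177, which rounds to 0.18
- Power at 0.18 = 81.2%

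The figure reproduces, so there is no arithmetic error.

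**3. Possible size of the bias.** For a binary high-ACE indicator, the crude bias in the HEU-HUU difference is g × d. Here g is the effect of high ACEs on TL in SD units, and d is the HEU minus HUU difference in prevalence. Neither is in the documents; the ranges are assumptions. The type I error of the nominal 5% test is 1 − Φ(1.960 − b/SE) + Φ(−1.960 − b/SE), with b = g × d.

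| g (SD) | d (points) | Bias (SD) | Share of 0.18 | Type I error |
|---|---|---|---|---|
| any | 0 | 0 | 0% | 5.0% |
| 0.1 | 5 | 0.005 | 3% | 5.1% |
| 0.1 | 30 | 0.03 | 17% | 7.6% |
| 0.3 | 10 | 0.03 | 17% | 7.6% |
| 0.3 | 20 | 0.06 | 33% | 15.8% |
| 0.3 | 30 | 0.09 | 50% | 29.6% |
| 0.5 | 5 | 0.025 | 14% | 6.8% |
| 0.5 | 30 | 0.15 | 83% | 66% |

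These are crude values. They take no credit for covariates already in the plan.

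**4. Precision after adding ACEs.** The adjusted detectable difference is 2.802 × 0.0632 × sqrt(v/(1 − r²)). Here r² = (p1 − p0)²/(4p(1 − p)), with p the mean prevalence, and v = 1 − g² × (mean within-group variance of the indicator).

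- Prevalence 45% vs 35%, g = 0.3: r² = 0.0104, v = 0.979, detectable difference 0.176.
- Prevalence 55% vs 25%, g = 0.2: r² = 0.0938, v = 0.991, detectable difference 0.185.

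Under these assumed inputs, adjustment leaves the detectable difference at about 0.18.

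**The case against.** The case on the other side has real weight.

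- **The second leg of confounding is not documented.** ACEs must differ by maternal HIV status, and the protocol never says they do. Section 8 says only that maternal stress and depression are prevalent among women living with HIV. This stands: without a gap the bias is zero.
- **The evidence on ACEs and TL is called limited.** This also stands; ACEs are a candidate determinant and not an established one. A rival explanation that is uncertain but already measured is still worth adjusting for.
- **Part of any bias is already handled.** Section 16 relies on recruitment from the same clinics, and the list includes maternal depression, education and household factors, which plausibly correlate with ACEs. This stands in part. Section 16 claims similar sociodemographics and reduced confounding, not balance on childhood adversity, and PHQ-9 measures depression, not childhood adversity.
- **The list is open and an SAP may complete it.** The cofactors are introduced as including the named items, TL is not in the protocol's Table 6 of outcomes, and nothing bars the use of ACEs. This lowers the urgency but does not dispose of the point. The protocol is not silent: it carries a stated list over to TL, beside an entry rule based on growth.

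A reader might infer that the TL comparison is confounded, or that a quarter to a half of the detectable difference would be spurious. The second figure follows from one choice of inputs: 0.3 × 0.15 = 0.045 and 0.3 × 0.30 = 0.09, divided by 0.18. Neither conclusion is supported. The documents give no ACE effect and no prevalence by HIV status, and the crude product ignores the covariates already planned. Nor would it be right to say that the study could not separate the two explanations, since ACEs are recorded and can be adjusted for.

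**Conclusion.** The omission and the unsuitable entry rule are clear from the text. The TL models inherit a covariate list without ACEs and a selection criterion tied to growth, although the TL paragraph cites evidence on ACEs and the enrolment visit records them.

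The consequence is conditional: residual confounding of the HEU-HUU TL difference is possible if ACEs differ by maternal HIV status. Over the assumed ranges the crude bias runs from 0.005 to 0.15 SD, or 3% to 83% of 0.18 SD, and it is zero with no gap. What remains after adjustment for depression, education and household factors cannot be worked out from the documents and may be smaller. The stated detectable difference is correct. The change is worth making because it costs almost nothing and protects the intended reading of TL as a marker of fetal HIV exposure.

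**What to change.** In the Telomere length analyses paragraph of section 12.c.vii:

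1. Pre-specify the enrolment maternal ACE score as a covariate in the TL models, whatever its association with growth.
2. State that the growth-based entry rule does not apply to TL models.
3. Report the HEU-HUU TL difference with and without the ACE term, so that readers can see how far it moves.

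IPV is named in the same sentence as ACEs but is not listed among the enrolment data, so it can be added only if it is in fact measured.

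The cost is a sentence or two of text and one or two degrees of freedom out of about 1000. No new data are required, the sample size is unchanged, and the detectable difference stays between about 0.176 and 0.185 SD under the assumptions in the working.
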